3	Total duration of all-cause IP stays	The total time in days of IP stays among patients who have at least 1 IP stay (continuous).	Start of data to 1 day before index date, index date until last recorded dose, and time from discontinuation through time of censoring
3	Total all-cause HCRU	IP, OP, ED, or pharmacy claims (dichotomous) Number of IP, OP, ED, or pharmacy claims	Start of data to 1 day before index date, index date until last recorded dose, and time from discontinuation through
3	MM-related IP visits	(continuous) Medical claim for IP (non-ED) visit with an MM ICD-10 code or treatment for MM (dichotomous) Number of IP (non-ED) visits with an MM	Start of data to 1 day before index date, index date until last recorded dose, and time from discontinuation through time of censoring
3	MM-related OP visits	ICD-10 code or treatment for MM (continuous) Medical claim for non-IP/non-ED visit with an MM ICD-10 code or treatment for MM (dichotomous)	Start of data to 1 day before index date, index date until last recorded dose, and time from
		Non-IP/non-ED visits with an MM ICD-10 code or treatment for MM (continuous)	discontinuation through time of censoring

	1		
3	MM-related pharmacy claims	Pharmacy claim with a treatment for MM (dichotomous)	Start of data to 1 day before index date, index date until last recorded dose, and time from
		Number of pharmacy claims with a treatment for MM (continuous)	discontinuation through time of censoring
3	Total duration of MM-related IP stays	The total time in days of IP stays with an MM ICD-10 code or treatment for MM, among patients who have at least 1 IP stay (continuous)	Start of data to 1 day before index date, index date until last recorded dose, and time from discontinuation through time of censoring
3	Total MM-related HCRU	IP, OP, ED, or pharmacy claims with an MM ICD-10 code or treatment for MM (dichotomous)	Start of data to 1 day before index date, index date until last recorded dose, and time from discontinuation through
		IP, OP, ED, or pharmacy claims with an MM ICD-10 code or treatment for MM (continuous)	time of censoring
3	Cost of all-cause IP visits	Cost of IP (non-ED) visits (continuous)	Start of data to 1 day before index date, index date until last recorded dose, and time from discontinuation through time of censoring

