9.7. Data Analysis

This study will be largely descriptive in nature, and no formal statistical comparisons will be performed between groups. All characteristics and outcomes will be reported separately for each cohort. The number of patients who meet study eligibility criteria will be summarized in an attrition table. Inclusion and exclusion criteria will be listed hierarchically and the number of patients remaining at each step will be reported. Patient and treatment characteristics will be summarized using descriptive statistics. Categorical variables will be summarized by the number of available observations, frequency, percentage, and 95% confidence limits. Continuous variables will be summarized by the number of available observations, mean, standard deviation, 95% confidence limits, median, quartiles, minimum, and maximum, where appropriate. The prevalence and incidence, as well as the associated 95% confidence intervals (CI) for each adverse event, will be estimated. Kaplan-Meier methods will be used to estimate the median time to event, including 95% CIs for TTNT/D and OS. All-cause HCRU and MM-related HCRU will be measured as the mean, SD, median, IQR, minimum, and maximum of the total number of IP, OP, ED, and pharmacy claims. Given the variable follow-up time available for each patient, HCRU and costs will be reported, for instance, on a per-patient-per-month (PPPM) basis. Relative Administration Intensity (RAI) will be calculated as the ratio of the actual number of administrations during each time period divided by the expected number of administrations based on the label for the treatment.

Based on the study cohorts of interest, patients may be characterized by the following attributes of interest:

- Demographic characteristics such as age, sex, race/ethnicity, state, and region
- Reason for Medicare enrollment
- Social determinants of health such as household income, education level, marital status, and home ownership

PFIZER CONFIDENTIAL

- Clinical characteristics such as comorbidity and past treatment status
- Healthcare resource utilization such as hospitalization and place of service distribution

Subgroup analysis will identify samples of patients based on reason for Medicare entitlement: disabled beneficiaries, beneficiaries with end-stage renal disease (ESRD), and beneficiaries aged 65 to 115 years qualifying by age.

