9.7.3. Healthcare Resource Utilization and Cost

All-cause HCRU and MM-related HCRU (i.e., HCRU with a diagnosis code or treatment for MM) will be measured as the total number of per-patient-per-month (PPPM) IP, OP, ED, and pharmacy claims that occurred over the follow-up period. Medical claims will only be counted once per day to estimate visits. Additionally, the total length of IP stays will be reported among patients with at least one IP visit. Given the recency of the study period, costs will not be adjusted for inflation.

HCRU and costs will be measured across three different time periods: from the start of data to a day before the index date, from the index date until last recorded dose, and the time from discontinuation through the time of censoring. Patients will be censored at the earliest of death, next treatment (CART, BsABs, bendamustine or belantamab), the end of part A or B continuous closed-claim coverage, or the end of data.

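### Total inpatient days have no time denominator and cover only patients with a stay, so figures for three unequal windows partly measure window length

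*Protocol*

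**What the plan says.** Table 3 in Protocol 9.3 defines the all-cause duration variable as "The total time in days of IP stays among patients who have at least 1 IP stay (continuous". The MM-related variable has the same form (cut here before its last noun): "The total time in days of IP stays with an MM ICD-10 code or treatment for MM, among patients who have at least 1 IP". Neither row has a time denominator. Both are assessed over "Start of data to 1 day before index date, index date until last recorded dose, and time from discontinuation through time of censoring".

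Section 9.7.3 puts the numbers of inpatient, outpatient, ED and pharmacy claims on a per-patient-month basis. It then adds that "the total length of IP stays will be reported among patients with at least one IP visit", over the same three windows. Section 9.7 has one general sentence: "Given the variable follow-up time available for each patient, HCRU and costs will be reported, for instance, on a per-patient-per-month (PPPM) basis".

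Section 9.2 gives a different baseline window for utilization, namely the 180 days before index up to index. Table 3 and 9.7.3 go back to the start of data.

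**The concern.** A sum of days grows with the time over which it is taken. The three windows differ in length from patient to patient and from one another, and the subset of patients with at least one stay changes with the window. The figure therefore mixes hospitalization intensity with observation time.

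Inpatient use belongs to primary Objective 3. The same measure is repeated for teclistamab and at successive data cuts, where time on treatment can lengthen simply because follow-up does. A table of before, on and after treatment invites a comparison that these totals cannot support. The rows for any use, yes or no, depend on window length in the same way.

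**Working it through.** The protocol states no figure for inpatient days or window lengths, so there is nothing of its own to reproduce. The check asks what the stated definition returns when the true rate is known.

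**Inputs from the protocol**
- Start of data 1 January 2016; index from 14 August 2023 to March 2025 (9.2; 31 March used here); data to December 2025 (9.1; 31 December used here).
- 1 month = 30.4375 days (9.7.5).
- Enrollment required: 180 days before index and 30 days after (9.2.1).

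**Calendar limits of the windows**
- Pre-index: 2,782 / 30.4375 = 91.4 months for the earliest index date, and 3,377 / 30.4375 = 110.9 months for the latest. Only 180 / 30.4375 = 5.9 months of enrollment is guaranteed.
- All time after index: at most 870 / 30.4375 = 28.6 months (earliest index) or 275 / 30.4375 = 9.0 months (latest).

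**Assumptions, not in the documents**
- Poisson admissions at λ = 0.02, 0.05 or 0.10 per month.
- Mean stay L = 6 days.
- 3, 6 or 12 months on treatment.
- Observed pre-index time of 5.9 to 110.9 months.

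**Formula.** Expected total days among patients with at least one stay in a window of T months:

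E = λTL / (1 − exp(−λT))

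**Equal true rates, λ = 0.05, 6 months on treatment**

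On treatment: 0.3 × 6 / (1 − exp(−0.3)) = 1.8 / 0.259 = 6.9 days.

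| Observed pre-index months | Pre-index E (days) | Pre-index / on-treatment |
|---|---|---|
| 91.4 | 27.7 | 4.0 |
| 60 | 18.9 | 2.7 |
| 24 | 10.3 | 1.5 |
| 5.9 (180 days) | 6.9 | 1.0 |

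With 12 months on treatment and 5.9 months before index, the ratio is 6.9 / 8.0 = 0.87, so the direction reverses.

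**Range over λ.** Equal rates, 91.4 to 110.9 months before index and 3 to 12 months on treatment:
- λ = 0.02: 1.9- to 2.4-fold
- λ = 0.05: 3.5- to 5.2-fold
- λ = 0.10: 5.3- to 9.6-fold

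**Higher true rate on treatment** (λ = 0.05 before index, 91.4 months before, 6 months on):
- Doubled: 27.7 against 8.0 days, still 3.5-fold lower on treatment.
- Tripled: 27.7 against 9.1 days, still 3.0-fold lower.

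**Longer time on treatment at a constant rate** (λ = 0.05): 6.5, 6.9 and 8.0 days at 3, 6 and 12 months. This is the drift to expect between data cuts, or between cohorts with different time on treatment.

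**Any-stay rows.** P = 1 − exp(−λT). At λ = 0.05 this is 99% over 91.4 months, 70% over 24 months and 26% over 6 months, at one and the same rate.

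**With a time denominator.** Days per patient-month over all patients is λTL / T = λL = 0.05 × 6 = 0.30 in every window, whatever its length. A doubled or tripled true rate then shows as a ratio of 2.0 or 3.0.

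**The case against.** The best reply is that 9.7 already promises per-patient-month reporting of utilization, that Table 3 does not name that scale for visit counts or costs either, and that detailed summaries are left to a SAP that is not shown. This has some force: the protocol nowhere excludes scaling of inpatient days. But the sentence in 9.7 gives the monthly basis only as an example and does not name inpatient days. The specific text in 9.7.3 scales the claim counts and then introduces total length as a separate item. Someone programming from this text would produce unscaled totals.

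Three further points stand and limit the concern. The study is descriptive, with no formal test between groups. Per-patient-month inpatient visit counts are reported alongside, although visits are not days. Showing the share of patients with any use is ordinary description and misleads only when compared across unequal windows.

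A reader might infer something stronger: that the plan will make an unchanged or higher burden on treatment look several-fold lower. One example would be 1/12 stay per month with 6 days per stay. That gives 50.0 days over 100 pre-index months against 7.1 over 4 treated months at equal rates, and 10.9 on treatment at four times the rate. The arithmetic is right, but it needs about 100 observed months before index. The protocol guarantees 180 days, and 9.2 names 180 days as the baseline window. There the same model gives 7.6 days against 7.1 at equal rates and 7.6 against 10.9 at four times the rate, with no reversal.

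A reader might also infer that patients with only non-MM stays enter the MM-related row as zeros. That is one reading; the wording can equally mean at least one MM-related stay. It is ambiguous, not a shown error.

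**Conclusion.** The point holds as a defect of definition. Total inpatient days are specified without time scaling, only among patients with a stay, over windows of unequal length, and no binding sentence elsewhere corrects this. The totals partly measure window length and should not be read across windows, cohorts or data cuts.

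The size is conditional. At 0.05 stays per month, 6 days per stay, equal true rates and 6 months on treatment, the pre-index figure is about 4.0 times the on-treatment figure with 91.4 months observed, 1.5 times with 24 months and equal with 180 days. It can reverse when time on treatment exceeds observed pre-index time. Admission rate, stay length, observed enrollment and treatment duration are all assumed. No hypothesis test is affected; the risk is a misleading descriptive result under a primary objective. The conflict over the baseline window between 9.2 and Table 3/9.7.3 largely decides how big the distortion is.

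**What to change.** - In Table 3 and 9.7.3, report all-cause and MM-related inpatient days per observed (enrolled) patient-month, over all patients in the window, zeros included.
- Keep length per admission as a supplement, or keep the conditional total provided that the person-time of each window is shown beside it.
- State that the MM-related conditional row is among patients with at least one MM-related stay.
- Reconcile the 180-day baseline utilization window in 9.2 with the start-of-data window in Table 3 and 9.7.3.
- Show the yes/no rows beside the person-time of each window, or over a short fixed window that the enrollment criteria cover, for example 30 days. A 180-day window after index would bring back unequal observation: 9.2.1 requires only 30 days of enrollment after index, and 9.7.3 censors at death or next treatment.

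The cost is wording in 9.2, Table 3 and 9.7.3. The per-patient-month claim counts already need the person-months, so no new data are required.

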Exploratory Obj 1	Cytokine release syndrome (CRS) ¹	Medical claim with an ICD-10 code in the inpatient, non-IP or pharmacy setting for CRS, categorized into the following grades (categorical): • Any (all grades and unspecified grade) • Grade 1 • Grade 2 • Grade 3 • Grade 4 • Grade 5 If patients have multiple, conflicting grades, then the highest recorded grade will be reported	Index date to end of follow-up, where follow-up will be based on last dose of elranatamab or teclistamab (e.g., 14 days after last recorded dose or 90 days after last recorded dose).
Exploratory Obj 1	Cytokine release syndrome (CRS) ¹ symptoms	Medical claim with an ICD-10 code in the inpatient, non-IP or pharmacy setting for CRS symptoms, per a algorithmic type approach (e.g., Keating algorithm, identifying patients with fever, hypotension, fatigue, headaches, hypoxia)	Index date to end of follow-up, where follow-up will be based on last dose of elranatamab or teclistamab (e.g., 14 days after last recorded dose or 90 days after last recorded dose).
Exploratory Obj 1	Immune effector cell-associated neurotoxicity syndrome (ICANS)	Medical claim with evidence of an ICD-10 code in the inpatient, non-IP or pharmacy setting for ICANS, categorized into the following grades (categorical): • Any (all grades and unspecified grade) • Grade 1 • Grade 2 • Grade 3 • Grade 4 • Grade 5 If patients have multiple, conflicting grades then the highest recorded grade will be reported	Index date to end of follow-up, where follow-up will be based on last dose of elranatamab or teclistamab (e.g., 14 days after last recorded dose or 90 days after last recorded dose).
Hematologic	events		
Exploratory Obj 1	Anemia ¹	Medical claim with an ICD-10 code in the inpatient, non-IP, or pharmacy setting for anemia (dichotomous)	Index date to end of follow-up, where follow- up will be based on last dose of elranatamab or teclistamab (e.g., 14 days after last recorded dose or

			90 days after last recorded dose).
Exploratory Obj 1	Lymphopenia ¹	Medical claim with an ICD-10 code in the inpatient, non-IP, or pharmacy setting for lymphopenia (dichotomous)	Index date to end of follow-up, where follow-up will be based on last dose of elranatamab or teclistamab (e.g., 14 days after last recorded dose or 90 days after last recorded dose).
Non-hematol	ogic events		
Exploratory Obj 1	Hypogammaglobuli nemia ¹	Medical claim with an ICD-10 code in the inpatient, non-IP, or pharmacy setting for hypogammaglobulinemia (dichotomous)	Index date to end of follow-up, where follow-up will be based on last dose of elranatamab or teclistamab (e.g., 14 days after last recorded dose or 90 days after last recorded dose).
Exploratory Obj 1	Hypophosphataemia	Medical claim with an ICD-10 code in the inpatient, non-IP, or pharmacy setting for hypophosphatemia (dichotomous)	Index date to end of follow-up, where follow-up will be based on last dose of elranatamab or teclistamab (e.g., 14 days after last recorded dose or 90 days after last recorded dose).
Exploratory Obj 1	Hypokalaemia ¹	Medical claim with an ICD-10 code in the inpatient, non-IP, or pharmacy setting for hypokalemia (dichotomous)	Index date to end of follow-up, where follow-up will be based on last dose of elranatamab or teclistamab (e.g., 14 days after last recorded dose or 90 days after last recorded dose).
Exploratory Obj 1	Hepatotoxicity ¹	Medical claim with an ICD-10 code in the inpatient, non-IP, or pharmacy setting for hepatotoxicity (dichotomous)	Index date to end of follow-up, where follow- up will be based on last dose of elranatamab or teclistamab (e.g., 14 days after last recorded dose or

			90 days after last recorded dose).
Exploratory Obj 1	Renal failure ²	Medical claim with an ICD-10 code in the inpatient, non-IP, or pharmacy setting for renal failure (dichotomous)	Index date to end of follow-up, where follow-up will be based on last dose of elranatamab or teclistamab (e.g., 14 days after last recorded dose or 90 days after last recorded dose).
Exploratory Obj 1	Peripheral neuropathy ¹	Medical claim with an ICD-10 code in the inpatient, non-IP, or pharmacy setting for peripheral neuropathy (dichotomous)	Index date to end of follow-up, where follow-up will be based on last dose of elranatamab or teclistamab (e.g., 14 days after last recorded dose or 90 days after last recorded dose).
Exploratory Obj 1	Arthralgia ³	Medical claim with an ICD-10 code in the inpatient, non-IP, or pharmacy setting for arthralgia (dichotomous)	Index date to end of follow-up, where follow-up will be based on last dose of elranatamab or teclistamab (e.g., 14 days after last recorded dose or 90 days after last recorded dose).
Exploratory Obj 1	Pyrexia ³	Medical claim with an ICD-10 code in the inpatient, non-IP, or pharmacy setting for pyrexia (dichotomous)	Index date to end of follow-up, where follow-up will be based on last dose of elranatamab or teclistamab (e.g., 14 days after last recorded dose or 90 days after last recorded dose).
Exploratory Obj 1	Hypotension ³	Medical claim with an ICD-10 code in the inpatient, non-IP, or pharmacy setting for hypotension (dichotomous)	Index date to end of follow-up, where follow-up will be based on last dose of elranatamab or teclistamab (e.g., 14 days after last recorded dose or 90 days after last recorded dose).

	T		
Exploratory Obj 1	Fatigue ³	Medical claim with an ICD-10 code in the inpatient, non-IP, or pharmacy setting for fatigue (dichotomous)	Index date to end of follow-up, where follow-up will be based on last dose of elranatamab or teclistamab (e.g., 14 days after last recorded dose or 90 days after last recorded dose).
Exploratory Obj 1	Nausea or vomiting ³	Medical claim with an ICD-10 code in the inpatient, non-IP, or pharmacy setting for nausea or vomiting (dichotomous)	Index date to end of follow-up, where follow-up will be based on last dose of elranatamab or teclistamab (e.g., 14 days after last recorded dose or 90 days after last recorded dose).
Exploratory Obj 1	Diarrhea ³	Medical claim with an ICD-10 code in the inpatient, non-IP, or pharmacy setting for diarrhea (dichotomous)	Index date to end of follow-up, where follow-up will be based on last dose of elranatamab or teclistamab (e.g., 14 days after last recorded dose or 90 days after last recorded dose).
Exploratory Obj 1	Rash ³	Medical claim with an ICD-10 code in the inpatient, non-IP, or pharmacy setting for rash (dichotomous)	Index date to end of follow-up, where follow-up will be based on last dose of elranatamab or teclistamab (e.g., 14 days after last recorded dose or 90 days after last recorded dose).
Exploratory Obj 1	Angioedema ³	Medical claim with an ICD-10 code in the inpatient, non-IP, or pharmacy setting for angioedema (dichotomous)	Index date to end of follow-up, where follow-up will be based on last dose of elranatamab or teclistamab (e.g., 14 days after last recorded dose or 90 days after last recorded dose).
Exploratory Obj 1	Erythema ³	Medical claim with an ICD-10 code in the inpatient, non-IP, or pharmacy setting for erythema (dichotomous)	Index date to end of follow-up, where follow- up will be based on last

	1	Т	
			dose of elranatamab or teclistamab (e.g., 14 days after last recorded dose or 90 days after last recorded dose).
Exploratory Obj 1	Muscle spasms ³	Medical claim with an ICD-10 code in the inpatient, non-IP, or pharmacy setting for muscle spasms (dichotomous)	Index date to end of follow-up, where follow-up will be based on last dose of elranatamab or teclistamab (e.g., 14 days after last recorded dose or 90 days after last recorded dose).
Exploratory Obj 1	Musculoskeletal pain ³	Medical claim with an ICD-10 code in the inpatient, non-IP, or pharmacy setting for musculoskeletal pain (dichotomous)	Index date to end of follow-up, where follow-up will be based on last dose of elranatamab or teclistamab (e.g., 14 days after last recorded dose or 90 days after last recorded dose).
Infections			
Exploratory Obj 1	COVID-19 ²	Medical claim with an ICD-10 code in the inpatient, non-IP, or pharmacy setting for COVID-19 (dichotomous)	Index date to end of follow-up, where follow-up will be based on last dose of elranatamab or teclistamab (e.g., 14 days after last recorded dose or 90 days after last recorded dose).
Exploratory Obj 1	Adenoviral pneumonia ²	Medical claim with an ICD-10 code in the inpatient, non-IP, or pharmacy setting for adenoviral pneumonia (dichotomous)	Index date to end of follow-up, where follow-up will be based on last dose of elranatamab or teclistamab (e.g., 14 days after last recorded dose or 90 days after last recorded dose).
Exploratory Obj 1	Cytomegaloviral pneumonitis ²	Medical claim with an ICD-10 code in the inpatient, non-IP, or pharmacy setting for cytomegaloviral pneumonitis (dichotomous)	Index date to end of follow-up, where follow-up will be based on last dose of elranatamab or

			teclistamab (e.g., 14 days after last recorded dose or 90 days after last recorded dose).
Exploratory Obj 1	COVID-19 pneumonia ²	Medical claim with an ICD-10 code in the inpatient, non-IP, or pharmacy setting for COVID-19 related pneumonia (dichotomous)	Index date to end of follow-up, where follow-up will be based on last dose of elranatamab or teclistamab (e.g., 14 days after last recorded dose or 90 days after last recorded dose).
Exploratory Obj 1	Other pneumonia ²	Medical claim with an ICD-10 code in the inpatient, non-IP, or pharmacy setting for pneumonia other than adenoviral or cytomegaloviral pneumonia (dichotomous)	Index date to end of follow-up, where follow-up will be based on last dose of elranatamab or teclistamab (e.g., 14 days after last recorded dose or 90 days after last recorded dose).
Exploratory Obj 1	Upper respiratory tract Infection ²	Medical claim with an ICD-10 code in the inpatient, non-IP, or pharmacy setting for upper respiratory tract infection (dichotomous)	Index date to end of follow-up, where follow-up will be based on last dose of elranatamab or teclistamab (e.g., 14 days after last recorded dose or 90 days after last recorded dose).
Exploratory Obj 1	Sepsis ²	Medical claim with an ICD-10 code in the inpatient, non-IP, or pharmacy setting for sepsis (dichotomous)	Index date to end of follow-up, where follow-up will be based on last dose of elranatamab or teclistamab (e.g., 14 days after last recorded dose or 90 days after last recorded dose).
Exploratory Obj 1	Cytomegaloviral infection ²	Medical claim with an ICD-10 code in the inpatient, non-IP, or pharmacy setting for cytomegaloviral infection (dichotomous)	Index date to end of follow-up, where follow- up will be based on last dose of elranatamab or teclistamab (e.g., 14 days after last recorded dose or

			90 days after last recorded dose).
Exploratory Obj 1	PJP ²	Medical claim with an ICD-10 code for PJP (dichotomous)	Index date to end of follow-up, where follow-up will be based on last dose of elranatamab or teclistamab (e.g., 14 days after last recorded dose or 90 days after last recorded dose).
Exploratory Obj 1	Hepatitis C ²	Medical claim with an ICD-10 code in the inpatient, non-IP or pharmacy setting for hepatitis C (dichotomous)	Index date to end of follow-up, where follow-up will be based on last dose of elranatamab or teclistamab (e.g., 14 days after last recorded dose or 90 days after last recorded dose).
Exploratory Obj 1	Hepatitis B ²	Medical claim with an ICD-10 code in the inpatient, non-IP or pharmacy setting for hepatitis B (dichotomous)	Index date to end of follow-up, where follow-up will be based on last dose of elranatamab or teclistamab (e.g., 14 days after last recorded dose or 90 days after last recorded dose).
Exploratory Obj 1	Other infectious hepatitis ²	Medical claim with an ICD-10 code in the inpatient, non-IP or pharmacy setting for infectious hepatitis (other than hepatitis B or C) (dichotomous)	Index date to end of follow-up, where follow-up will be based on last dose of elranatamab or teclistamab (e.g., 14 days after last recorded dose or 90 days after last recorded dose).
Exploratory Obj 1	Helicobacter pylori ²	Medical claim with an ICD-10 code in the inpatient, non-IP or pharmacy setting for helicobacter pylori (dichotomous)	Index date to end of follow-up, where follow-up will be based on last dose of elranatamab or teclistamab (e.g., 14 days after last recorded dose or 90 days after last recorded dose).

Exploratory Obj 1	Candida esophagitis ²	Medical claim with an ICD-10 code in the inpatient, non-IP or pharmacy setting for candida esophagitis (dichotomous)	Index date to end of follow-up, where follow-up will be based on last dose of elranatamab or teclistamab (e.g., 14 days after last recorded dose or 90 days after last recorded dose).				
Exploratory Obj 1	Urinary tract infection ²	Medical claim with an ICD-10 code in the inpatient, non-IP or pharmacy setting for a urinary tract infection (dichotomous)	Index date to end of follow-up, where follow-up will be based on last dose of elranatamab or teclistamab (e.g., 14 days after last recorded dose or 90 days after last recorded dose).				
Exploratory Obj 1	Time to infection onset	Time in days from index date to first infection for the following infections:	Index date until censor				
Effectiveness	Effectiveness						
Exploratory Obj 2	os	Time (in months) from index date until date of death (continuous)	Index date until censor				
Exploratory Obj 2	TTNT/D	Time (in months) from index date until the date of the next treatment (CAR-T, BsABs, bendamustine or belantamab) or death (continuous)	Index date until censor				

- 1. Variable will be measured as incident and prevalent. Incident cases have 30-day washout period applied
- 2. Variable will be measured as incident and prevalent. Incident cases have 60-day washout period applied
- 3. Variable will be measured as incident and prevalent. Incident cases have 14-day washout period applied

